Exploratory Obj 1	Cytomegaloviral pneumonitis ²	Medical claim with an ICD-10 code in the IP, non-IP, or pharmacy setting for cytomegaloviral pneumonitis (dichotomous)	Index date to end of follow-up, where follow-up will be based on last dose of elranatamab (eg, 14 days after last recorded dose or 90 days after last recorded dose).

			
See Section 9.7.6 for censoring criteria

Exploratory Obj 1	Other pneumonia ²	Medical claim with an ICD-10 code in the IP, non-IP, or pharmacy setting for pneumonia other than adenoviral or cytomegaloviral pneumonia (dichotomous)	
Index date to end of follow-up, where follow-up will be based on last dose of elranatamab (eg, 14 days after last recorded dose or 90 days after last recorded dose).
 
See Section 9.7.6 for censoring criteria

Exploratory Obj 1	Upper respiratory tract infection ²	Medical claim with an ICD-10 code in the IP, non-IP, or pharmacy setting for upper respiratory tract infection (dichotomous)	
Index date to end of follow-up, where follow-up will be based on last dose of elranatamab (eg, 14 days after last recorded dose or 90 days after last recorded dose).
 
See Section 9.7.6 for censoring criteria

Exploratory Obj 1	Sepsis ²	Medical claim with an ICD-10 code in the IP, non-IP, or pharmacy setting for sepsis (dichotomous)	
Index date to end of follow-up, where follow-up will be based on last dose of elranatamab (eg, 14 days after last recorded dose or 90 days after last recorded dose).
 
See Section 9.7.6 for censoring criteria

Exploratory Obj 1 Exploratory Obj 1	Cytomegaloviral infection ²	Medical claim with an ICD-10 code for PJP (dichotomous)	
Index date to end of follow-up, where follow-up will be based on last dose of elranatamab (eg, 14 days after last recorded dose or 90 days after last recorded dose).
 
See Section 9.7.6 for censoring criteria

Exploratory Obj 1	PJP ²	Medical claim with an ICD-10 code for PJP (dichotomous)	Index date to end of follow-up, where follow-up will be based on last dose of elranatamab (eg, 14 days after last recorded dose or 90 days after last recorded dose). See Section 9.7.6 for censoring criteria

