			G62.89, G61.9, G62.9, H46.3, M54.10, M54.18, M79.2, R20.0, R20.1, R20.2, R20.3, R20.8, R20.9	
Any infection	Baseline characteristic - Clinical	Claims data	An ICD-10 Diagnosis Code for any of the following types of infections. See the rows below for codes for each infection type. COVID-19, Adenoviral pneumonia, Cytomegaloviral pneumonitis, Other Pneumonia, Upper respiratory tract infection, Sepsis, Cytomegaloviral infection, PJP, Hepatitis C, Hepatitis B, Other infectious hepatitis, Helicobacter pylori, Candida esophagitis, Urinary tract infection	N/A
Use of intravenous anti-infective	Baseline characteristic - Clinical	Claims data	See “Antivirals,” “Antibiotics,” and “Antifungals” and where service category = injection/infusion drugs or where route = injectable or route array has injectable in it OR HCPCS/CPT codes that indicate IV administration of an anti-infective	N/A
Absolute neutrophil count (for Neutropenia)	Baseline characteristic - Clinical, AE	Claims data	White blood cell count x the percentage of neutrophils White blood cell count: Results_value in the lab results table where the result_abbrev is wbc and result_units are thousand per μ L Percent Neutrophil: Results_value in the lab results table where the result_abbrev is neutrophils percent and result_units are percent White blood cell count and percent neutrophil results must occur on the same day	Severe Chronic Neutropenia International Registry
Neutropenia	Baseline characteristic - Clinical, AE	Claims data	ICD-10 Diagnosis: D70.x or Absolute neutrophil count < 1500 cells per μ L	Kim et al. (2022) Lustberg et al. (2012)

PFIZER CONFIDENTIAL

Redacted

Hypercalcemia	Baseline characteristic - Clinical	Claims data	ICD-10 Diagnosis: E83.52 or value in the GDD table where test is hypercalcemia and result_units are mg/dL and result_value is > 11.5	Kumi et al. (2024) CTCAE v6 (2020)
Hepatotoxicity	Baseline characteristic - Clinical, AE	Claims data	ICD-10 Diagnosis: K71.x	Banerjee et al. (2023)
Amyloidosis	Baseline characteristic - Clinical	Claims data	ICD-10 Diagnosis: E85.4x, E85.8x, E85.9x	Quock et al. (2018)
Hypertension	Baseline characteristic - Clinical	Claims data	ICD-10 Diagnosis: I10x-I15x	Angier et al. (2019)
Extramedullary plasmacytoma	Baseline characteristic - Clinical	Claims data	ICD-10 Diagnosis: C90.2x	Ellington et al. (2021)
CCI score	Baseline characteristic - Clinical	Claims data	See components below	Glasheen et al. (2019)

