Myocardial infarction	Baseline characteristic - Clinical	Claims data	ICD-10 Diagnosis: I21.x, I22.x, I25.2	Glasheen et al. (2019)
Congestive heart failure	Baseline characteristic - Clinical	Claims data	ICD-10 Diagnosis: I11.0, I13.0, I13.2, I25.5, I42.0, I42.5, I42.6, I42.7, I42.8, I42.9, I43.x, I50.x, P29.0	Glasheen et al. (2019)
Peripheral vascular disease	Baseline characteristic - Clinical	Claims data	ICD-10 Diagnosis: I70.x, I71.x, I73.1, I73.8, I73.9, I77.1, I79.0, I79.1, I79.8, K55.1, K55.8, K55.9, Z95.8, Z95.9	Glasheen et al. (2019)

Cerebrovascular disease	Baseline characteristic - Clinical	Claims data	ICD-10 Diagnosis: G45.x, G46.x, H34.0x, H34.1x, H34.2x, I60.x, I61.x, I62.x, I63.x, I64.x, I65.x, I66.x, I67.x, I68.x	Glasheen et al. (2019)
Dementia	Baseline characteristic - Clinical	Claims data	ICD-10 Diagnosis: F01.x, F02.x, F03.x, F04, F05, F06.1, F06.8, G13.2, G13.8, G30.x, G31.0x, G31.1, G31.2, G91.4, G94, R41.81, R54	Glasheen et al. (2019)
Chronic pulmonary disease	Baseline characteristic - Clinical	Claims data	ICD-10 Diagnosis: J40.x, J41.x, J42.x, J43.x, J44.x, J45.x, J46.x, J47.x, J60.x, J61.x, J62.x, J63.x, J64.x, J65.x, J66.x, J67.x, J68.4, J70.1, J70.3	Glasheen et al. (2019)
Rheumatic disease	Baseline characteristic - Clinical	Claims data	ICD-10 Diagnosis: M05.x, M06.x, M31.5, M32.x, M33.x, M34.x, M35.1, M35.3, M36.0	Glasheen et al. (2019)
Peptic ulcer disease	Baseline characteristic - Clinical	Claims data	ICD-10 Diagnosis: K25.x, K26.x, K27.x, K28.x	Glasheen et al. (2019)
Mild liver disease	Baseline characteristic - Clinical	Claims data	ICD-10 Diagnosis: B18.x, K70.0, K70.1, K70.2, K70.3, K70.9, K71.3, K71.4, K71.5, K71.7, K73.x, K74.x, K76.0, K76.2, K76.3, K76.4, K76.8, K76.9, Z94.4	Glasheen et al. (2019)
Moderate or severe liver disease	Baseline characteristic - Clinical	Claims data	ICD-10 Diagnosis: I85.0x, I86.4, K70.4x, K71.1x, K72.1x, K72.9x, K76.5, K76.6, K76.7	Glasheen et al. (2019)
Diabetes without chronic complications	Baseline characteristic - Clinical	Claims data	ICD-10 Diagnosis: E08.0x, E08.1x, E08.6x, E08.8x, E08.9x, E09.0x, E09.1x, E09.6x, E09.8x, E09.9x, E10.0x, E10.1x, E10.6x, E10.8x, E10.9x, E11.0x, E11.1x, E11.6x, E11.8x, E11.9x, E13.0x, E13.1x, E13.6x, E13.8x, E13.9x	Glasheen et al. (2019)

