Musculoskeletal pain	AE	Claims data	ICD-10 Diagnosis: M25.50, M25.522, M25.551, M25.552, M25.561, M25.562, M25.572, M25.579, M25.59, M25.612, M25.621, M25.629, M25.631, M25.641, M25.642, M25.652, M25.661, M25.662, M25.669, M25.671, M25.673, M25.674, M25.675, M25.676, M54.6, M54.81, M79.1, M79.12, M79.18, M79.621, M79.622, M79.631, M79.639, M79.641, M79.644, M79.646, M79.652, M79.659, M79.661, M79.662, M79.669, M79.671, M79.673, M79.675, M25.511, M25.512, M25.519, M25.521, M25.529, M25.531, M25.532, M25.539, M25.541, M25.542, M25.549, M25.559, M25.569, M25.571, M25.60, M25.611, M25.619, M25.622, M25.632, M25.639, M25.649, M25.651, M25.659, M25.672, M25.69, M54.89, M54.9, M79.10, M79.11, M79.601, M79.602, M79.603, M79.604, M79.605, M79.606, M79.609, M79.629, M79.632, M79.642, M79.643, M79.645, M79.651, M79.672, M79.674, M79.676	Clinical Classifications Software Refined for ICD-10-CM
COVID-19	AE - infection	Claims data	ICD-10 Diagnosis: U07.1	Pfaff et al. (2023)
Adenoviral pneumonia	AE - infection	Claims data	ICD-10 Diagnosis: J12.0	Cocoros et al. (2024)

Cytomegaloviral pneumonitis	AE - infection	Claims data	ICD-10 Diagnosis: B25.0	ICD-10data.com
Other pneumonia	AE - infection	Claims data	ICD-10 Diagnosis: J12.1, J12.2, J12.81, J12.3, J12.89, J12.9, J13, J18.1, J15.0, J15.1, J14, J15.4, J15.3, J15.20, J15.211, J15.212, J15.29, J15.8, J15.5, J15.6, A48.1, J15.9, J15.7, J16.0, J16.8, A37.01, A37.11, A37.81, A37.91, A22.1, B44.0, J17, B77.81, J18.0, J18.8, J18.9, J10.00, J10.01, J10.08, J11.00, J11.08	Smithee et al. (2020)
Pneumonia	AE - infection	Claims data	An ICD-10 Diagnosis Code for any of the following types of pneumonia. See the following rows for infection type: Adenoviral pneumonia, cytomegaloviral pneumonia, other pneumonia	
Upper respiratory tract infection	AE - infection	Claims data	ICD-10 Diagnosis: A38.0-A38.9, J02.0-J03.91, J01.00-J01.91, J09.x1-J11.89, J00, J04.0-J06.9, H65.00-H65.199, H68.011-H68.019, J20.0-J20.9, J45.20-J45.998, J45.21, J45.31, J45.41, J45.51, J45.901	Butler et al. (2023)
Acute sinusitis	AE - infection	Claims data	ICD-10 Diagnosis: J01.x0	Savage et al. (2023)
Bronchitis	AE - infection	Claims data	ICD-10 Diagnosis: J20.0-J20.9	Butler et al. (2023)
Sepsis	AE - infection	Claims data	ICD-10 Diagnosis: A02.1, A22.7, A26.7, A32.7, A40.0, A40.1, A40.3, A40.8, A40.9, A41.01, A41.02, A41.1, A41.2, A41.3, A41.4, A41.50, A41.51, A41.52, A41.53, A41.59, A41.81, A41.89, A41.9, A42.7, A54.86, B37.7, R65.20, R65.2	Prasad et al. (2021)

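### The upper respiratory tract infection code list contains the full asthma range, so asthma claims are counted as infections on treatment and at baseline

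*Protocol*

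**What the plan says.** Section 9.3 of the protocol refers the reader to Annex 2 for the full code list. Section 9.8 says that variables will be coded from the protocol's codes and that the protocol will be strictly followed.

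- **Annex 2, upper respiratory tract infection.** The list includes an influenza block, "J09.x1-J11.89, J00, J04.0-J06.9", then acute bronchitis and asthma, "H68.011-H68.019, J20.0-J20.9, J45.20-J45.998". It closes with "J45.20-J45.998, J45.21, J45.31, J45.41, J45.51, J45.901".
- **Annex 2, chronic pulmonary disease (Charlson component).** The list includes "J40.x, J41.x, J42.x, J43.x, J44.x, J45.x, J46.x, J47.x".
- **Annex 2, bronchitis (a separate adverse event).** "ICD-10 Diagnosis: J20.0-J20.9".
- **Annex 2, other pneumonia (a separate adverse event).** The list ends with "J10.00, J10.01, J10.08, J11.00, J11.08".
- **Annex 2, any infection (baseline).** The components include "COVID-19, Adenoviral pneumonia, Cytomegaloviral pneumonitis, Other Pneumonia, Upper respiratory tract infection, Sepsis". Bronchitis is not among them, although Table 2 lists it.
- **Table 3.** URTI is a yes/no adverse event met by a claim with a listed code. It is reported as prevalent and incident, with a 60-day washout for incidence.
- **Table 2.** Any infection is a yes/no variable assessed from myeloma diagnosis to the day before index.

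**The concern.** One annex gives the same asthma claim two meanings: a chronic comorbidity in the Charlson index and an infection in the safety table. Asthma is not an infection, and a routine visit for long-standing asthma says nothing about infection on treatment. The protocol cites infections as the most frequent of the pivotal-trial adverse events it lists (69.9%, Section 7), and the abstract names them among the events to be reported. An infection row that also counts a chronic airway disease cannot be read at face value. The baseline infection history has the same fault, over a look-back that can reach to the start of data in January 2016. The teclistamab cohort uses the same list.

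The URTI row also holds acute bronchitis codes and influenza-with-pneumonia codes. These are infections, but of the lower tract, so the row's label does not describe its content.

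**Working it through.** The protocol gives no URTI or asthma rate, so there is no planned figure to reproduce. The check compares code lists and then illustrates the possible size.

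**Step 1: overlap of the Annex 2 lists**

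| Block in the URTI row | Also classed in Annex 2 as | Overlap |
|---|---|---|
| J45.20-J45.998 | Chronic pulmonary disease (J45.x) | The range lies wholly inside J45.x |
| J45.21, J45.31, J45.41, J45.51, J45.901 | Same | All 5 already lie inside the range |
| J20.0-J20.9 | Bronchitis | 10 of 10 codes |
| J09.x1-J11.89 | Other pneumonia | 5 of its 41 codes: J10.00, J10.01, J10.08, J11.00, J11.08 |

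The J09 pneumonia code (J09.x1) is in the URTI row but not in the other pneumonia row.

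**Step 2: what an asthma claim does to each output**

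1. *URTI prevalence (Section 9.7.6).* The numerator is patients with an event and no washout applies. An asthma claim in either follow-up window (to 14 or 90 days after the last administration) makes the patient a case. The error can only raise the figure.
2. *URTI incidence.* A patient with long-standing asthma, an asthma claim in follow-up and no listed claim in the preceding 60 days becomes a false incident case. A patient whose asthma claim falls in the washout is not counted. If that patient then has a true URTI, it is lost from the numerator. The false cases push incidence up, and the lost cases partly offset this.
3. *Baseline any infection.* One asthma claim between myeloma diagnosis and index is enough. The error can only raise the figure.
4. *Time to infection onset (Table 3).* URTI is not among the infections listed, so this output is unaffected.

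**Step 3: illustration of size for prevalence (assumed inputs)**

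Let t be the true URTI proportion, and a the proportion with an asthma claim in follow-up among patients without URTI. Then

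reported = t + (1 − t) × a

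| t | a = 3% | a = 10% | Relative excess |
|---|---|---|---|
| 10% | 0.10 + 0.90 × 0.03 = 12.7% | 0.10 + 0.90 × 0.10 = 19.0% | 27% to 90% |
| 15% | 0.15 + 0.85 × 0.03 = 17.55% | 0.15 + 0.85 × 0.10 = 23.5% | 17% to 57% |
| 25% | 0.25 + 0.75 × 0.03 = 27.25% | 0.25 + 0.75 × 0.10 = 32.5% | 9% to 30% |

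Neither t nor a comes from the documents. The table covers asthma only.

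**The case against.** The strongest defence is that the effect is narrow. Safety is an exploratory objective, no formal comparison is planned, and Table 3 has no pooled on-treatment infection outcome. The damage is therefore confined to one adverse event row and one baseline yes/no variable that already pools many infections. All of that stands, and it limits the priority. It does not make the asthma codes correct. The limitation stated in Section 9.9, provider miscoding, does not cover them either: here a correctly coded asthma visit becomes an infection.

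The row also cites a published source that is not at hand, and that source may have had a reason for the codes. Whatever the reason, the protocol applies them under the URTI label with no qualification.

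A reader might infer more than the documents support:

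- *That bronchitis and influenza pneumonia are double-counted.* Each adverse event is a separate percentage and no sum across rows is planned. Other rows overlap too: pneumonia pools three rows, cytomegaloviral disease (B25.x) contains cytomegaloviral pneumonitis (B25.0), and M25.5x arthralgia codes recur under musculoskeletal pain. Appearing in two rows is not a miscount.
- *That lower-tract codes corrupt the baseline infection variable.* Table 2 intends bronchitis and pneumonia to count there, so they are true positives. Only asthma corrupts that variable.
- *That the five redundant single codes show what was meant.* They may point to a narrower list, but this is inference. The conflict between the two Annex 2 rows stands without it.
- *That the relative excess is an estimate.* It follows entirely from assumed rates.

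**Conclusion.** The point holds for asthma. The URTI list conflicts with the annex's own classification of J45.x. Followed strictly, it records asthma claims as infections in URTI prevalence, URTI incidence and baseline any infection, in both cohorts. For prevalence and the baseline variable the direction is certain: upward or no change. For incidence the list adds false cases, with some offset through the washout. The documents do not allow the size to be computed. The 17.55% to 23.5% range depends on an assumed true URTI of 15% and an asthma-claim share of 3% to 10% among patients without URTI.

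For J20.0-J20.9 and the influenza-with-pneumonia codes, the fault is one of labelling: true lower-tract infections are reported as upper-tract. This should be corrected before publication because the problem is plain and cheap to remove, but it does not touch the primary objectives.

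**What to change.** 1. Delete all J45 codes, both the range and the five single codes, from the URTI row of Annex 2. Re-run URTI prevalence and incidence and baseline any infection in both cohorts.
2. Remove J20.0-J20.9 from the URTI row. In the same edit, add bronchitis explicitly to the Annex 2 row for any infection, as Table 2 has it. Under the Annex version acute bronchitis currently enters that variable only through the URTI list, so removing it alone would lose true infections.
3. Remove the influenza-with-pneumonia codes from the URTI row. J10.0x and J11.0x stay under other pneumonia. Move the J09 pneumonia code to other pneumonia; simply deleting it would drop those patients from every infection row.

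The cost is a code-list edit and a re-run, which can be taken up with a planned refresh (the last is dated 20 December 2025) before the final report of 28 February 2026. URTI prevalence and baseline any infection will stay the same or fall. Moving the J09 code may slightly raise other pneumonia and pooled pneumonia, and so may affect time to pneumonia onset. If earlier refreshes used the same list, the report should say that their URTI and baseline infection figures are not comparable with the corrected ones.
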